#### Data Analysis

SAS or R software, or an equivalent software package will be used for statistical analysis.

Descriptive statistics will be provided for all parameters. The statistics will be appropriate for the type of data:

- For continuous and count variables, statistics will include the number of observations, mean, standard deviation, median, minimum, maximum, and 95% confidence interval (CI).
- For categorical variables, the descriptive statistics will include the count and percent of observations in each category along with its 95% CI. The denominator for the percentages will also be presented as the number of subjects in the analysis population.

This is a non-interventional, observational study, therefore only CI are calculated. If data transformations are used, they will be specified in the final clinical study report. All endpoints will be analyzed by the appropriate type of descriptive statistic(s) as described above.

All variables will be analyzed in an exploratory manner. No formal statistical hypothesis testing will be performed.

#### **Populations for Data Analysis**

The Intention-to-treat (ITT) population includes all patients who have received at least one dose of Vertigoheel® and have at least one post-baseline measurement.

As data collection will be based on routine clinical practice so that no stipulations will be made on assessments as well as on study visits, a PP population will not be defined. Protocol deviations (as far as known), e.g. deviations from the in-/exclusion criteria, will be listed.

The Safety population includes all patients who have received at least one dose of Vertigoheel®. Clinical safety will be addressed by assessing AEs, physical examinations, vital signs in a descriptive manner.

Effectiveness analyses will be performed with the ITT population, safety analyses with the Safety population.

## 9 DATA MANAGEMENT

#### **Data Source**

Data for this study will be obtained from various sources, including treating physicians and source documentation such as questionnaires and examination methods for vertigo. The investigator will record relevant medical data, participation in the study and the occurrence of adverse events. Treatment related data during visits that take place in routine practice will be collected as source data in the respective patient's records. The outcomes will be captured from validated examination methods for vertigo (i.e. posturography, vHIT, caloric testing). The investigator must keep supportive original source documentation for all patient-related data.

#### **Data collection**

Data will be collected using an eCRF that is specifically designed for this study and must match the source data. The data will be pseudonymized, processed and stored according to local law. This also allows preservation for future use. The investigator has ultimate responsibility for the accuracy, authenticity, timely collection and reporting of all data entered on the CRFs. For the duration of the study and afterwards, only the patient's treating physician or authorized site personnel can identify the patient based on the patient identification code. All these data may only be entered and updated in the CRFs by authorized study personnel. eCRFs must be completed for each patient, who provided informed consent.

#### **Data Quality Assurance**

The EDC system will be fully validated to ensure that it meets the scientific, regulatory, and logistical requirements of the study before it is used to capture data from this study. Before using the EDC system, all users will receive training on the system and study-specific training. After they are trained, users will be provided with individual system access rights. Data will be reviewed for consistency by data management using both automated logical checks and manual review. All data collected will be approved by the investigator at the investigational center. This approval acknowledges the investigator's review and acceptance of the data as being complete and accurate.

### **Quality Control/Data Validation**

All procedures must follow Good Clinical Practice (GCP), existing standard operating procedures (SOP) and local laws and regulations as applicable. Details concerning data management procedures and query management will be described in a data management and data validation plan. Using an electronic CRF an audit trail will be maintained to provide an electronic record of which data were entered or subsequently changed, by whom and when Checks will be implemented to review the data entered into the clinical database for completeness, and to review the data for completeness, consistency and plausibility. The checks to be programmed will be specified in the data validation plan. After running the check programs, the resulting queries will be sent to the investigator for clarification. Logical checks will be implemented to ensure data quality and accuracy. Any necessary changes will be made in the clinical database, and data review and validation procedures will be repeated as needed. At the conclusion of the study, the EDC system and all other study data will be locked to further additions or corrections. Locking the study data represents the acknowledgement that all data have been captured and confirmed as accurate.

## **10 PUBLICATIONS**

The sponsor is responsible for ensuring that the public has access to the appropriate information about the study by conforming to local and regional requirements and regulations for registration and posting of results. The sponsor is responsible for the preparation of a non-interventional study report. The final study report is signed by the sponsor.

Publication of any data, including abstracts, presentations, and manuscripts, will follow Good Publication Practices.

The purpose of this statistical analysis plan (SAP) is to ensure that the data listings, summary tables, and figures which will be produced, and the statistical methodologies that will be used, are complete and appropriate to allow valid conclusions regarding the trial objectives.

The SAP outlines the following:

- Study objectives
- Study design
- Variables analyzed and analysis sets
- Statistical methods regarding trial drug exposure, effectiveness analysis, concomitant medications, adverse events handling, laboratory data, vital signs and physical examinations
- Tables, Listings, Figures (TLFs)
- This SAP is based on the Observational Plan, Final Version 1, dated 28-JUN-2021 and pCRF Final Version 1, dated 23-NOV-2021.

1.1 Responsibilities

The Sponsor or a delegate will perform the statistical analyses.

2 OBJECTIVES

2.1 Primary Objectives

- To evaluate the change in PRO 2±1 month after baseline versus baseline for patients suffering from functional dizziness (FD) and bilateral vestibulopathy (BVP) treated with Vertigoheel® in German clinical practice.

2.2 Secondary Objectives

- To evaluate the change from baseline in QoL after 2±1 month of routine Vertigoheel® treatment measured by questionnaires
- To evaluate the change from baseline in postural imbalance after 2±1 month of routine Vertigoheel® treatment for patients suffering from FD and BVP
- To evaluate the change from baseline in psychiatric symptoms after 2±1 month of routine Vertigoheel® treatment for patients suffering from FD measured by questionnaires

3 METHODOLOGY

3.1 Study Design

This study is an open-label, prospective, monocenter non-interventional study. It is set up for descriptive purposes.

All study activities are consistent with the EU Directive 2001/20/EC section for non-

interventional studies as follows:

- The study drug is prescribed in the usual manner in accordance with the terms of the marketing authorization/SmPC.
- The assignment of the patient to a particular therapeutic strategy is not defined by the observational plan but falls into the responsibility of the treating physician.
- No extra means of interventions that would not otherwise be used, will be applied to the patients.

Patients are observed for 2±1 month under Vertigoheel® treatment.

3.2 Study Population

Patients with BVP and FD are recruited from the Department of Neurology and the German Center for Vertigo and Balance Disorders at the Hospital of the LMU, Munich.

As this is a prospective, non-interventional study, the study population is composed of male and female patients, aged between 18 and 80 years old, diagnosed with BVP or FD. There are no specific patient withdrawal criteria for this non-interventional study except for the common ones as loss of market authorization.

3.4 Inclusion Criteria

Patients are included in the study if they meet all the following criteria

- Treatment with Vertigoheel® has been chosen by the physician independently of including the patient in this non-interventional study.
- BVP or FD (according to the current diagnostic criteria of the Bárány Society (2017)-FD
- Symptoms for > 3 months of moderate to severe intensity according to the DHI [0 (minimum score) -100 (maximum score)] of 30 to 90 points.
- ≥18 – 80 years of age
- Legally competent male or female outpatient
- Signed informed consent
- Not pregnant (as proven by negative pregnancy test in case of woman of childbearing potential before first study drug administration) or breast-feeding

3.5 Exclusion Criteria

Patients are not included in the study if any of the following criteria applies

- Having taken within the last 2 months or currently taking Vertigoheel®
- Debilitating acute or chronic illness (i.e. psychiatric illnesses)
- History of sensitivity to any component of the study drug under observation
- Unwilling or unable to comply with all the requirements of the study protocol
- Any relationship of dependence with the sponsor or with the investigator
- At the discretion of the investigator

Patients with contraindications according to current SmPC must not be included, observed, or documented in this non-interventional study.

4 STUDY FLOW CHART

Procedure	Visit 0 Month 0 Baseline	Visit 1 Month 2 +/- 1 after Baseline						
Evaluations / Recordings								
Patient informed consent	x							
Assignment of patient number	x							
Inclusion/exclusion criteria	x							
Physical examination including vital signs (heart rate, blood pressure)	x	x						
Demographics, from Visit 1 documentation of changes vs. baseline for variable demographic parameters	x	x						
Medical and medication history vertigo-related	x	x						
Concomitant diseases/medications, from Visit 1 documentation of changes vs. baseline	x	x						
Procedure (continued)								
Evaluations / Recordings								

DHI		x	x			
Posturography		x	x			
FD: PHQ-9, GAD-7		x	x			
BVP: vHIT, caloric testing		x	x			
Quality of life (EQ-5D-5L)		x	x			
Review of Vertigoheel administration		x	x			
Adverse events / Serious Adverse Events			x			
Patients who stopped therapy (reasons for d/c, date of last intake)			x			
		Close Out Documentation				

5 STATISTICAL ANALYSIS

Due to the non-interventional design, this study is set-up for descriptive purposes, no a priori hypothesis will be tested, and no comparisons will be made with other products or treatments.

This is a non-interventional study. It is planned that 20 patients with BVP and 40 patients with FD participate in the observational period for 2-months treatment. Due to the small number of patients enrolled, no interim analysis is planned.

5.1 Sample Size Calculation

Sample size calculations were performed for confidence intervals for different paired means. When the sample size is 20, a two-sided 95% CI for the difference between paired means will extend 0.351 from the observed difference in means. For a smaller CI a higher n is needed, i.e. n=25 (28 with 10% drop-out) distance from mean to limit 0.314, n=30 (33 with 10% drop-out) distance from mean to limit 0.265, n=40 (44) – 0.248.

- Significance level 0.05 (2-sided)
- 95% confidence intervals will be calculated to estimate treatment effects
- Standard deviation of 0.8 for both indications
- Lost to follow-up 10%
- Power: 80%

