Milestones	
 
under observation.
 
Unwilling or unable to comply with all the requirements of the study protocol.
 
Any relationship of dependence with the sponsor or with the investigator.
 
Sept 21 FPI, July 22 LPO, DBL Aug 22.
 

Statistical Methods	
 
Previous trial with Vertigoheel®
 
Weiser et al. (1998) The efficacy and safety evaluation of Vertigoheel® vs betahistine hydrochloride demonstrated a reduction of 2 score points of the mean intensity of vertigo attacks with a standard deviation of 0.8 score points and a non-inferiority limit of 20%. Power: 80%.
 
Current study
 
Significance level 0.05 (2-sided)
 
95% confidence intervals will be calculated to estimate treatment effects
 
Standard deviation of 0.8 for both indications
 
Lost to follow-up 10% (BVP) or 20% to 30% (FD) Power: 80%
 
(Please see 8.1)
 

Sample Size Calculations and Power Calculations	Sample size calculations have been performed for confidence intervals for different paired means. When the sample size is 20, a two-sided 95% CI for the difference between paired means will extend 0.351 from the observed difference in means. For a smaller CI a higher n is needed, i.e. $n=25$ (28 with 10% drop-out) distance from mean to limit 0.314, $n=30$ (33 with 10% drop-out) distance from mean to limit 0.265, n=40 (44) – 0.248.

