### Sample Size Calculation

Sample size calculations have been performed for confidence intervals for different paired means. When the sample size is 20, a two-sided 95% CI for the difference between paired means will extend 0.351 from the observed difference in means. For a smaller CI a higher n is needed, i.e. n=25 (28 with 10% drop-out) distance from mean to limit 0.314, n=30 (33 with 10% drop-out) distance from mean to limit 0.265, n=40 (44) – 0.248.

- Significance level 0.05 (2-sided).
- 95% confidence intervals will be calculated to estimate treatment effects.
- Standard deviation of 0.8 for both indications.
- Lost to follow-up 10%.
- Power: 80%.

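### The planned 95% CI half-widths of 0.351, 0.314 and 0.248 treat the SD as known; with an SD estimated from the data, t-based half-widths are 3% to 7% wider

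*SAP*

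**What the plan says.** SAP 5.1 bases the sample size on the width of a confidence interval for a paired mean difference. For 20 patients it says that "a two-sided 95% CI for the difference between paired means will extend 0.351 from the observed difference in means". It then lists what larger numbers would give: "n=25 (28 with 10% drop-out) distance from mean to limit 0.314", "n=30 (33 with 10% drop-out) distance from mean to limit 0.265", and 0.248 for 40 patients (44 with drop-out). The inputs are a two-sided 5% level and "Standard deviation of 0.8 for both indications". The protocol gives the same half-widths in its summary and in the sample size part of section 8.

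None of these places names the quantile used or says that the SD is taken as known. SAP 5.4 plans a mean, an SD and a two-sided 95% CI for every continuous variable. It names Clopper-Pearson for percentages but no method for the CI of a mean. Planned enrolment is 20 patients with BVP and 40 with FD (SAP 5; protocol section 8).

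**The concern.** The plan states how far the interval will reach as if that were fixed in advance. It would be fixed only if the SD were known to be 0.8 and the normal quantile were used. At the analysis, the SD will be estimated from roughly 20 or 40 patients per indication. The matching 95% interval for a mean then uses the t distribution with n − 1 degrees of freedom, which is wider.

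The study tests no hypothesis, so CI width is the only quantitative basis for its size. A reader who uses these figures to judge how precisely the study will estimate change is given values that are too favourable.

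**Working it through.** **Inputs.** Two-sided 95% CI; SD 0.8; n = 20, 25, 30 and 40 (SAP 5.1). The SD is read as that of the paired difference. The documents do not say so, but this reading reproduces three of the four stated figures.

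**Step 1: reproduce the plan's figures.** Normal-quantile half-width = 1.96 × 0.8/√n.

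- n=20: 1.96 × 0.1789 = 0.3506; stated 0.351, match.
- n=25: 1.96 × 0.1600 = 0.3136; stated 0.314, match.
- n=40: 1.96 × 0.1265 = 0.2479; stated 0.248, match.
- n=30: 1.96 × 0.1461 = 0.2863; stated 0.265, no match.

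The three matches identify the formula. The n=30 figure is a different kind of error: solving (1.96 × 0.8/0.265)² gives 35.0, so 0.265 is the normal-quantile value for 35 patients.

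**Step 2: t-based half-widths at the same SD.** Half-width = t(0.975, n − 1) × 0.8/√n.

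| n | t quantile | Stated | Normal | t-based | t against normal |
|---|---|---|---|---|---|
| 20 | 2.093 | 0.351 | 0.3506 | 0.374 | +6.8% |
| 25 | 2.064 | 0.314 | 0.3136 | 0.330 | +5.3% |
| 30 | 2.045 | 0.265 | 0.2863 | 0.299 | +4.3% |
| 40 | 2.023 | 0.248 | 0.2479 | 0.256 | +3.2% |

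None of the t-based values equals a stated one. The absolute gaps from the stated figures are 0.023 (n=20), 0.016 (n=25) and 0.008 (n=40). At n=30 the gap is 0.034, of which 0.286 − 0.265 = 0.021 comes from the separate n=30 error.

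**Step 3: what the t-based values mean.** They are the half-widths obtained if the observed SD is exactly 0.8. They are not averages over repeated studies. The sample SD is on average slightly below the true SD, so with a true SD of 0.8 the expected t half-widths are 0.370, 0.327, 0.296 and 0.254. These too exceed the normal-quantile values at every n.

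**Step 4: drop-out sizes at 10% loss.** 25/0.9 = 27.8, 30/0.9 = 33.3 and 40/0.9 = 44.4. Rounded to the nearest integer these are 28, 33 and 44, as printed. Rounded up they are 28, 34 and 45. Expected completers from the printed 33 and 44 are 33 × 0.9 = 29.7 and 44 × 0.9 = 39.6, short by 0.3 and 0.4 of a patient.

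**The case against.** The strongest reply is that a fixed planning SD with the normal quantile is a common approximation, that the gap is at most 0.023, and that no decision in a descriptive study turns on 0.351 against 0.374. The smallness is granted. The reply does not rescue the wording, which presents the approximation as what the interval will be and does not name it as an approximation.

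It can also be said that the 0.8 matters more than the quantile. The protocol gives 0.8 as the SD of vertigo-attack intensity in a previous trial, whereas its primary endpoint is change in DHI total on a 0–100 scale. That is true: the restated figures say no more about precision on the DHI than the present ones do. It is a separate question, and it does not make the arithmetic right.

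Three stronger readings are tempting, and the documents do not support them.

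- **Wrong drop-out formula.** A reader might infer that 33 and 44 come from multiplying by 1.1 where division by 0.9 was needed. Division by 0.9 with rounding to the nearest integer gives the same three printed sizes, and no formula is named. Only the rounding can be criticised.
- **Under-coverage of the reported intervals.** A reader might infer that the study's CIs will cover less than 95% because planning used 1.96. SAP 5.4 promises a two-sided 95% CI and nowhere says that 1.96 will be used. A planning formula is not evidence of the analysis formula.
- **A frequent miss of the stated width.** With a true SD of 0.8, a t interval at n=20 is wider than 0.351 in about 61% of studies. But it is wider than the corrected 0.374 in about 46%, simply because the sample SD varies. The choice of quantile accounts for about 16 percentage points, not 61.

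**Conclusion.** Wrong as written, and small in size. The half-widths for n = 20, 25 and 40 use the normal quantile with the SD treated as known, and the t-based half-widths at the same SD are 6.8%, 5.3% and 3.2% wider. The conclusion assumes that 0.8 is the SD of the paired difference and that CIs for means will be t intervals, which is appropriate with an estimated SD at these sizes but is not stated in the SAP.

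The point gives no ground for changing enrolment. The sizes 28, 33 and 44 illustrate what a narrower interval would need; the targets are 20 and 40, without inflation. Loss from those targets would widen the intervals further: at 10% loss, 18 and 36 completers give t half-widths of 0.398 and 0.271. That concerns attrition and is distinct from the quantile.

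**What to change.** In SAP 5.1, the protocol summary and protocol section 8:

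- Replace the half-widths with 0.374 (n=20), 0.330 (n=25), 0.299 (n=30) and 0.256 (n=40). The n=30 value also corrects 0.265.
- Describe them as the t-based half-width if the observed SD of the paired difference is 0.8. Do not call them expected half-widths; those would be 0.370, 0.327, 0.296 and 0.254 at a true SD of 0.8.
- Minor: if the drop-out sizes are kept, round n/0.9 up to 28, 34 and 45.

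Optionally, say in SAP 5.4 that CIs for means use the t distribution, so that the plan and the analysis visibly agree.

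The cost is a text change in three places and a slightly less favourable statement of precision. Enrolment and data collection stay as they are.

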5.2 Treatment Assignment and Blinding

A randomization code is not applicable as this is an open-label, prospective, monocenter non-interventional study.

5.3 Effectiveness Endpoints / Measurements

Since this is a non-interventional study, no differentiation between primary and secondary endpoints is made.

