	sensation of vertigo and dizziness as change from baseline
	to month $2\pm 1$ assessed by the Dizziness Handicap
	Inventory (DHI; total).
Secondary Endpoints	• Effect of Vertigoheel ® on QoL as change from baseline to
	month $2\pm 1$ assessed by EQ-5D-5L.
	• Effect of Vertigoheel ® on total sway path as change from
	baseline to month $2\pm 1$ assessed by static posturography.
	• In FD effect of Vertigoheel ® on psychiatric symptoms as
	change from baseline to month $2\pm 1$ assessed by Patient
	Health Ouestionnaire Mood Scale (PHO-9) and
	Generalized Anxiety Disorder Screener (GAD-7)
	• In BVP effect of Vertigoheel ® on vestibular function as
	change from baseline to month 2+1 assessed by video
	head impulse test (vHIT) and/or caloric testing
	• Adverse events (AFs)
	
 
Other observations related to safety (physical examination)
 

	and vital signs)
Study Design	Non-interventional observational prospective monocentric
Study Design	study
Study Population	It is planned to include 20 patients with BVP and 40 patients
	with ED who are going to start Vertigoheel ® treatment
	according to clinical practice at the study conter
	The desision of treatment is up to the physician's discretion
	The decision of treatment is up to the physician's discretion
Inclusion / Evolusion	and is to be made independent of this study.
Criteria	Following documentation criteria should be fulfilled
Cintoina	• BVP (according to the diagnostic criteria of the Bárány
	Society) or FD (according to the diagnostic criteria of the
	Bárány Society).
	• Symptoms for > 3 months of moderate to severe intensity
	according to the DHI [0 (minimum score) -100 (maximum
	score)] of 30 to 90 points.
	• $\geq 18 - 80$ years of age.
	• Legally competent male or female outpatient.
	Signed informed consent.
	• Not pregnant (as proven by negative pregnancy test in
	case of woman of childbearing potential before first
	study drug administration) or breast-feeding.
	Patients with the following conditions are excluded from the
	documentation in this NIS
	• Ongoing (within the last two months) or recently started
	Vertigoheel ® treatment.
	• Debilitating acute or chronic illness (e.g. psychiatric
1	
	illnesses).

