### **1.2 RATIONALE**

No systematic data in bilateral vestibulopathy and functional dizziness is available for Vertigoheel® regarding PRO and QoL in a real life setting in Germany. Nowadays, German health insurance is not only interested in direct costs, e.g. hospitalization, but also in patient reported and in clinical practice implemented outcome parameters. Therefore, patient-reported outcomes (PRO) as well as quality of life (OoL) assessed during clinical practice, were chosen as primary and secondary objectives respectively, to evaluate symptoms and QoL of Vertigoheel® treated patients in Germany. The current German AWMF guidelines for vestibular disorders (03/2021) recommend furthermore VOR, caloric testing, DHI and static posturography, as examinations for diagnosis and monitoring of the development for

patients with vertigo or dizziness.

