Appendix 1: Tables, Listings, Figures

Item No.	Title	Population	Content Description
14.1	Disposition, Baseline Characteristics, Medication and Further Analyses		
14.1.1	Patient disposition	All	Descriptive statistics on patients screened, failed screening, treated
14.1.2	Early termination	All	Descriptive statistics for early termination yes/no
14.1.3	Number of patients in each analysis population	All	Descriptive statistics for number and percentage of patients and reason for exclusion
14.1.4	Duration of study	All	Date of first patient in and last patient out of all patients
14.1.5	Duration of observation per patient	SP	Difference of Date of patient in and patient out per patient
14.1.6	Demographics and other baseline characteristics	ITT	Descriptive statistics of age, , height, weight, pregnancy test
14.1.7.1	Vital signs	ITT	Descriptive statistics of heart rate and blood pressure, at Screening Visit and 2±1 month after baseline
14.1.7.2	Physical examination	ITT	Descriptive statistics (normal, abnormal, ncs (not clinically significant), cs (clinically significant)), at Screening Visit and 2±1 month after baseline (shift table)
14.1.8.1	Primary diagnosis	ITT	Descriptive statistics of 
 - FD yes/no (derived from tick box 'NA' for caloric (BVP)) - BVP yes/no (derived from tick box 'NA' for GAD-7 (FD))
14.1.8.2	Medical history - Abuse history	ITT	Descriptive statistics of alcohol and drug consumption, smoking status
14.1.9.1	Treatment with Vertigoheel	SP	Descriptive statistics for 
 - Duration of treatment (date start of study – date start of Vertigoheel treatment - change of Vertigoheel dose yes/no
14.1.9.2	Prior medication	SP	Descriptive statistics for prior medication yes/no
14.1.9.2	Concomitant medication	SP	Descriptive statistics for change of concomitant medication yes/no
14.1.9.3	Product complaints	SP	Descriptive statistics for product complaint yes/no

14.2	Patient Reported Outcomes (Effectiveness)		
14.2.1	Primary Endpoint		
14.2.1	Dizziness Handicap Inventory	ITT	Descriptive statistics at Screening Visit and 2±1 month after baseline (yes, sometimes, no), and change from baseline to 2 months (shift table)
14.2.2	Secondary Endpoints		
14.2.2.1	Posturography	ITT	Descriptive statistics at Screening Visit and 2±1 month after baseline (normal, neuritis vestibularis, PPV), and change from baseline to 2±1 month after baseline (shift table)

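### SAP 5.3 drops the primary/secondary distinction that the protocol and the SAP's own objectives and table list keep, and the SAP never names the DHI total as an analysis variable

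*SAP*

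**What the plan says.** **Protocol.** The Observational Plan Summary gives a single primary endpoint, the change from baseline to month 2±1 in vertigo and dizziness symptoms, measured by the Dizziness Handicap "Inventory (DHI; total"). A separate row, "Secondary Endpoints", holds EQ-5D-5L, sway path, PHQ-9 and GAD-7 (FD), vHIT and/or caloric testing (BVP), and safety. Section 1.2 shows that the ranking was deliberate: patient-reported outcomes and quality of life "were chosen as primary and secondary objectives respectively".

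**SAP.** Section 5.3 states that, because the study is non-interventional, "no differentiation between primary and secondary endpoints is made". Yet the SAP has a section "2.1 Primary Objectives" on the patient-reported outcome, followed by separate secondary objectives in 2.2. Appendix 1 puts the DHI alone under "Primary Endpoint" and the other six effectiveness measures under a secondary heading. The content of the DHI row (Table 14.2.1) is: "Descriptive statistics at Screening Visit and 2±1 month after baseline (yes, sometimes, no), and change from baseline to 2 months (shift table").

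**The concern.** Two things are wrong, and they compound each other.

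First, the SAP takes two positions on whether there is a primary endpoint. Someone reporting the study could cite 5.3 to treat all measures alike, or Appendix 1 to lead with the DHI.

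Second, the SAP row that carries the primary label does not describe the protocol's primary quantity. A programmer who follows Table 14.2.1 literally would tabulate response categories and shifts. No mean change in DHI total need be produced.

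The study is single-arm and open-label, tests no hypothesis and reports only confidence intervals. In that setting, fixing the main result in advance is an important guard against giving prominence to whichever measure looks best once the data are seen. What is at stake is how the results are read, not an error rate.

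**Working it through.** The plan gives no figure to reproduce on this point, so the check is a comparison of texts.

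1. **Is there a primary endpoint?** Protocol summary: yes, the DHI total. Protocol 1.2: yes, as a deliberate choice. SAP 2.1 and 2.2: primary and secondary objectives are kept apart. SAP 5.3: no distinction. SAP Appendix 1: primary and secondary headings. Section 5.3 stands alone against every other place.

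2. **Does the stated reason explain the difference?** SAP 5.3 relies only on the non-interventional design. Protocol section 8 describes the same study as non-interventional and descriptive, without hypothesis tests, and the protocol still designates a primary endpoint. The reason therefore does not separate the two documents. Nothing in the SAP acknowledges or justifies a departure from the protocol.

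3. **Which DHI quantity does the SAP plan?**
   - 5.3.1 mentions 25 items and three sub-domains, but no total.
   - 5.4 lists the DHI among the shift tables, which cross the baseline category with the worst category after baseline.
   - Table 14.2.1 gives yes/sometimes/no. These are answer categories to single items and cannot be values of a score that runs from 0 to 100.
   - 3.4 uses the 0-100 score, but only as an entry criterion (30 to 90 points).
   - The Appendix 1 rows for PHQ-9 and GAD-7 do specify the total score. Two secondary measures thus have a named summary score, and the primary measure does not.

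4. **Could the general rules fill the gap?** Partly. 5.4 promises the mean, standard deviation and two-sided 95% CI for continuous variables and defines FD and BVP subgroups. 5.6.2 defines absolute change from baseline. Applied to the DHI total, these rules would give the protocol's estimate. No text says that they are to be applied to it.

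5. **How many measures compete for emphasis?** SAP 5.3.1 to 5.3.7 list seven instruments. Three apply to everyone (DHI, posturography, EQ-5D-5L), two only to FD (PHQ-9, GAD-7) and two only to BVP (vHIT, caloric testing), so each diagnosis group has 3 + 2 = 5. Appendix 1 plans posturography and vHIT as categories with shift tables and specifies no interval for a mean change in either.

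**The case against.** The strongest reply is that the hierarchy survives. The protocol names the DHI total, SAP 2.1 keeps a primary objective, and Appendix 1 puts only the DHI under the primary heading. An author who later promoted another measure would contradict both documents. This stands. A reader might infer from 5.3 that the SAP has abolished the primary endpoint or removed the only safeguard against selective reporting, but the documents do not support that. They show one sentence in conflict with the rest.

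A second reply is that the general rules in 5.4 and 5.6.2 already cover the DHI total. They could, so it would be wrong to say that the SAP cannot produce the estimate. But they do not say which DHI quantity is the endpoint, and the specific row points to categories.

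A reader might also attach a multiplicity percentage, namely the chance that at least one of several intervals excludes zero. The documents do not support one. Nothing is tested. The instruments are not independent, and independence would not give an upper bound. Each diagnosis group has five instruments rather than seven, and two of the seven are planned as categorical tables. Such a figure would also exist whether or not one endpoint carries the primary label.

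It can further be said that treating all endpoints alike is defensible in a purely descriptive single-arm study. As a general position it is, but this protocol chose otherwise and the SAP gives no reason that distinguishes it.

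Finally, the sentence in 5.3 and the row in Table 14.2.1 are separate defects, and correcting one does not correct the other. That is right, and the fix addresses both.

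**Conclusion.** The point holds as a contradiction together with a missing definition. SAP 5.3 is wrong as written: it conflicts with the protocol's primary endpoint and with the SAP's own objectives and table headings. Separately, the DHI total is never named as an analysis variable, so following the SAP literally need not produce the protocol's primary quantity.

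The consequence is ambiguity about the main result, and room for selective emphasis when an uncontrolled study is reported. It has no numerical size: no type I error rate is at stake and no percentage should be quoted. The conclusion rests on the wording of the two documents alone and on no assumption about variability, correlation or sample size. It should be corrected before analysis, but it does not threaten the data, because the DHI is scheduled at both visits.

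**What to change.** Replace the sentence in SAP 5.3 with: *Primary endpoint: change from baseline to month 2±1 in DHI total score (0-100), summarised by mean and two-sided 95% CI in each of the FD and BVP subgroups defined in 5.4. All other effectiveness endpoints are secondary.*

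Change Table 14.2.1 to report the DHI total at each visit and its change from baseline, and keep the item-level shift tables as supportive.

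This gives two primary estimates, one per diagnosis. Since nothing is tested, they can be reported side by side without an error-rate adjustment, but the SAP should say that both are shown and that neither is selected after the fact.

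The cost is one sentence and one table row. No new data are needed, and the change restores the protocol's own choice.
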